## 4. STUDY DESIGN

### 4.1 General study design and justification of design

The study will be conducted according to a Multi Centre, Post Market, Single-Arm, Open-Label, Interventional Study design, which is considered as the most appropriate for the collection of the clinical data about the safety and efficacy of the Endorail device in completing long-lasting diagnostic colonoscopy or surveillance colonoscopy. Considering that completion rate and adverse events occurrence are widely described in historical data from clinical studies and/or registries and may be used as objective for safety or effectiveness endpoints, the single-arm design can be considered sufficient for the aim of the study.

Outpatients of either sex aged between 22-75 years (inclusive), undergoing elective colonoscopy for diagnostic or surveillance colonoscopy, who have signed a written informed consent and presenting caecal intubation time greater than 10 minutes, will take part in the study. The study plan will include a screening/baseline/treatment visit (Visit 1/Day 1), during which colonoscopy with the investigational medical device Endorail will be performed and a phone follow-up visit (Visit 2), scheduled at 7 ( $\pm$  1) day after treatment with the investigational medical device Endorail.

### 4.2 Methods of minimizing bias

The following measures have been implemented in order to minimize avoid/bias:

- New technology bias is minimized through an adequate and thorough training to the endoscopist;
- Low statistical bias is minimized through an adequate estimate of the number of patients in the treatment group as compared to the state of the art;
- Multicentric study to minimize usability bias.

### 4.3 Eligibility criteria

#### Inclusion Criteria

1. Patients of both sexes aged between 22 – 75 years (inclusive);
2. Outpatients undergoing long-lasting diagnostic and surveillance colonoscopy; long-lasting colonoscopy is defined as follows: colonoscopy completion (caecal intubation) not achieved after 10 minutes from endoscope insertion through the anal canal;
3. Patients have given a written informed consent for participation in the study at the time of enrolment or before;
4. Patients able to understand the full nature and the purpose of the investigation, including possible risks and side effects, able to cooperate with the Investigator and to comply with the requirements of the entire investigation based on Investigator's judgement.

### Exclusion Criteria

1. Body mass index (BMI) > 30 kg/m^2;
2. Outpatients undergoing colonoscopy for colorectal cancer screening or therapeutic indication;
3. Patients in class >2 physical status of the classification system of American Society of Anaesthesiologists;
4. Any contraindications to colonoscopy;
5. Any contraindications to sedation;
6. Known allergy or hypersensitivity to any of the elements of the Endorail Set (e.g.: iron);
7. Patients with permanently or semi-permanently implanted medical devices, (e.g. orthopedic implants, trauma fixation devices, cardiac pacemakers, implantable cardioverter defibrillator, drug pumps, neurostimulators, vascular stents, cochlear implants, aneurysm clip);
8. Presence of dense diverticulosis
9. Presence of diverticulitis
10. Presence of ferromagnetic foreign body;
11. Presence of large abdominal hernias;
12. Urgent colonoscopy;
13. Presence of severe thrombocytopenia;
14. Presence of severe granulocytopenia;
15. Presence of severe coagulopathy;
16. Presence of peritonitis;
17. Presence of colonic wall ischemia or necrosis or injured mucosa; ;
18. Presence of peritoneal carcinomatosis;
19. Boston Bowel Preparation Scale <2 in at least one of the colonic segments;
20. Presence of obstructing masses and strictures of the colon;
21. History of total or subtotal colectomy.
22. Presence of angulated and fixed colon curves;
23. Pregnant or breast-feeding women;
24. Patient unable to provide the signed informed consent, uncooperative patient or patient unlikely to comply with the protocol or unable to understand the nature, scope and possible consequences of the study;
25. Presence of any other reason that, in the opinion of the investigator, prevents the subject from participating in the study or compromises the subject safety
26. Concomitant participation in other clinical investigations or participation in the evaluation of any investigational product/device in the 30 days before this study or previous participation in the same investigation;
27. Urgent colonoscopy.

#### **4.4 Recruitment and screening**

Before starting the recruitment, each investigator must be familiar with the device under investigation.

If the Investigator has never used the Endorail device, he/she should perform at least three colonoscopy procedures with Endorail. To assess the performance case, the Investigator should sign a self-declaration titled “Performance case declaration” stating that the three cases have been duly performed in compliance with Protocol requirement.

Before any screening procedure all patients must sign a written informed consent for the study. The following logs must be maintained at each study site and kept in the Investigator Site File: a “Subject Screening Log\Enrolment Log”, to document the identification of subjects who enter screening and to document chronological enrolment of patients, a “Subject Identification List” for all subjects registered to maintain the correlation with the patient's full identification data (name, surname - confidential).

Eligible patients who have provided written informed consent to study participation and that satisfy all inclusion criteria and none of the exclusion criteria both detailed in Section 4.3, will be enrolled in the clinical study.

Eligibility will be determined by the investigator basing on standard colonoscopy clinical history and colonoscopy indication. Enrolment will be completed during colonoscopy if caecal intubation time is longer than 10 min.

When the investigator registers in the eCRF the enrolment of a new patient, the eCRF will assign a 4-digit identification number to each patient included in the investigation. The patient number will be sequentially assigned to each patient who signs the informed consent, starting from 0001. If a subject discontinues from the study, the patient number will not be re-used, and the subject will not be allowed to re-enter the study. Moreover, to distinguish the patient number of different sites involved in the clinical trial, the 4 digit patient number will be preceded by a 2-digit site number. Before the study initiation, the Sponsor will assign to each participating site its unique 2-digit site number.

#### **4.5 Criteria for withdrawal / discontinuation of participants**

Patients have the right to withdraw from the investigation at any time for any reason including personal reasons (consent withdrawal). The Investigator also has the right to withdraw any patient from the investigation if he/she deems this appropriate and in the best interest of the patients.

Possible reasons to discontinue a patient from the study include:

- Patients' withdrawal of consent for study participation;
- Adverse events (AEs): occurrence of unexpected symptoms during the study, whose intensity or specific treatments require the discontinuation of the colonoscopy with the investigational product. The reason of discontinuation must be recorded in the medical records and in the eCRF. If necessary, patients will be given an appropriate symptomatic treatment that will be recorded in the medical records and in the eCRF, together with the outcome and the duration of the AE. In case of serious adverse reactions to the investigational device, the study sponsor must be advised within 24 hours and all procedures for the reporting of serious adverse events (SAEs) will be made effective;

- Protocol violation: at least one of the conditions that represent any of the exclusion criteria (refer to Section 4.3). The reason of discontinuation must be recorded in the medical records and in the eCRF;
- The Investigator considers the study procedure discontinuation as appropriate, in the best interest of the patient;
- The Sponsor will terminate the study for any reason (refer to Section 4.6);
- Patient dies during the study: the reason and the date of death will have to be recorded in the medical records and in the eCRF, together with the Investigator's opinion on the correlation between the cause of death and the investigational product.

Should a patient decide to withdraw from the study, all efforts will be made to complete and report the observations as thoroughly as possible. A complete final evaluation at the time of the withdrawal (study end-point) should be performed, and a clear, univocal explanation of the reason why the subject is withdrawn from the study should be reported in the medical record.

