### 8.2 Determination of Sample Size

Efficacy (first primary objective) will be assessed by measuring the colonoscopy completion rate in long-lasting procedures, which is a measurable parameter of clinical value recognized by international medical societies. Safety (second primary objective) will be assessed by measuring the rare of adverse events. They are classified into: serious gastrointestinal events; myocardial infarction; stroke; pneumonia. Based on the literature [30]; their occurrence rates in screening or surveillance colonoscopy are 47 persons, 4 persons, 7 persons and 10 persons per 100'000, respectively.

These two objectives are merged in one indicator, which is equal to 1 for each subject if the procedure is incomplete or an adverse event occurs, and 0 otherwise.

The non-completion rate of long-lasting colonoscopies conducted with Endorail is expected to be around 10%. This will be compared to the above-mentioned threshold of 20% for incomplete procedures. It should be noted that this threshold is conservative and represents the most critical setting for comparison with respect to the state of the art, as it is derived from the lower bound of the range from the literature.

When including the safety to provide the expected value of the indicator for Endorail and the corresponding threshold, the above values of 10% minimally change, as the adverse event

occurrence rate is 0.068% (given by the sum of the occurrence of the 4 events reported above per 100'000 persons, expressed in percentage).

With a significance level  $\alpha$  of 5%, assuming a proportion of outcome of 10.1%, 85 patients allow to test with a power of 80% the  $H_0: p \geq 20\%$  vs  $H_1: p < 20\%$ , where 20% is the estimated percentage of incomplete procedure from literature.

The chosen number is then increased by the 10% to account for possible drop-out (e.g., cases to be discarded, losses to follow-up, etc.), resulting in  $85/0.90 = 95$  patients to be actually enrolled.

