#### **8.4.1 Datasets to be analysed, analysis populations**

- Screening set: will include all patients who have signed the informed consent and have been screened for inclusion in the study;
- Intention-to-treat population (ITT): will include all enrolled patients who have started treatment with Endorail;
- Per-Protocol (PP) population: will include all patients of the ITT who also meet all inclusion/exclusion criteria and who do not have any major protocol deviation, to be defined in a data review meeting (DRM) of the Sponsor, Contract research Organization (CRO) representatives and the biostatistician.

Analysis will be performed on the ITT population and will be repeated in the PP population. The results obtained in the PP population will be seen as confirmative of those observed in the ITT population.

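### Exclusion criteria that can themselves cause a failed intubation have no assessment cut-off, so the per-protocol set can lose failures after the outcome is known, and the ITT wording should be tightened to rule this out

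*Combined protocol and SAP*

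**What the plan says.** **Exclusions.** Section 4.3 excludes patients with "Boston Bowel Preparation Scale <2 in at least one of the colonic segments" (criterion 19), obstructing masses or strictures (20) and "Presence of angulated and fixed colon curves" (22), besides dense diverticulosis (8) and injured mucosa (17). Criterion 22 has no objective definition.

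**When they are judged.** Section 4.4 states: "Eligibility will be determined by the investigator basing on standard colonoscopy clinical history and colonoscopy indication". It enrols only patients who meet no exclusion criterion, and completes enrolment during the procedure once 10 minutes have passed. Section 6.2.1 lists the criteria review before sedation and insertion. Its bullet saying that patients can be enrolled comes after the one on performing and completing the colonoscopy.

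**What follows if one is found.** Section 4.5 gives as a reason for discontinuation "Protocol violation: at least one of the conditions that represent any of the exclusion criteria". Section 5.4 keeps patients whose study intervention is permanently discontinued under evaluation for efficacy and safety. Section 4.7 allows replacement only for consent withdrawal before completion and for loss to follow-up.

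**Analysis sets.** In section 8.4.1 the ITT set is the enrolled patients in whom Endorail treatment was started, with no eligibility condition. The PP set "will include all patients of the ITT who also meet all inclusion/exclusion criteria" and have no major deviation, as defined at a data review meeting that includes the sponsor. The analysis is done on ITT, repeated on PP, and the PP result is described as confirming it. Section 8.2 allows for "cases to be discarded, losses to follow-up, etc" without saying which cases may be discarded.

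**The concern.** The primary efficacy outcome is caecal intubation. A stricture, a fixed angulated curve or poor preparation is both an exclusion criterion and a plausible explanation for not reaching the caecum. By inclusion criterion 2 the caecum has not been reached at 10 minutes, so segments proximal to the scope tip are unseen when Endorail is started. Preparation there cannot yet have been scored, and in an incomplete case some segments never are.

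An eligibility finding can therefore arise after the device has been used and has failed, and be made by an operator who knows the result. A failure invites a search for its cause; a completed case does not. If such findings count as eligibility violations, failures leave the analysis set more readily than successes, and the observed incompletion rate falls with no effect of the device.

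**Working it through.** **1. The plan's own figure.** Section 8.2: one-sided significance level "of 5%, assuming a proportion of outcome of 10.1%, 85 patients allow to test with a power of 80"%, against a null rate of 20%, "where 20% is the estimated percentage of incomplete procedure from literature". The normal approximation gives

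n = [(1.645·√(0.20·0.80) + 0.842·√(0.101·0.899)) / (0.20 − 0.101)]² = 84.8, so 85; then 85/0.90 = 94.4, so 95.

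The stated numbers reproduce. Section 8.4 plans a one-tailed exact binomial test, with p = P(X ≤ x), X ~ Bin(n, 0.20). Success needs at most 10 events in 85 (exact type I error 3.3%) or at most 12 in 95 (4.2%).

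**2. Sensitivity to single cases.** Removing failures takes them from both numerator and denominator:

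| Treated | p | After removal | p |
|---|---|---|---|
| 11/85 | 0.063 | 10/84 (one removed) | 0.037 |
| 12/85 | 0.108 | 10/83 (two removed) | 0.041 |
| 13/85 | 0.172 | 10/82 (three removed) | 0.046 |
| 4/38 (first interim) | 0.099 | 3/37 (one removed) | 0.045 |

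The drop-out allowance that includes discarded cases is 95 − 85 = 10 patients, more than any removal in this table.

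**3. Effect on false success.** Assumptions:
- the true event rate is 20%, so the device does nothing;
- each failure is reclassified as ineligible with probability q, and no success is;
- N patients are treated and the reduced set is retested at one-sided 5%, in a single look.

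N is the number treated, because section 4.7 provides no replacement for ineligibility. The rate in the reduced set is 0.2(1 − q)/(1 − 0.2q). The false-success probability is the sum, over x failures and d removals, of Bin(x; N, 0.2)·Bin(d; x, q) wherever P(X ≤ x − d | N − d, 0.2) ≤ 0.05.

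| q | Rate in reduced set | Expected removals, N = 85 | False success, N = 85 | False success, N = 95 |
|---|---|---|---|---|
| 0 | 20.0% | 0 | 3.3% | 4.2% |
| 10% | 18.4% | 85·0.2·0.1 = 1.7 | 7.8% | 7.9% |
| 20% | 16.7% | 3.4 | 14.6% | 15.4% |
| 30% | 14.9% | 5.1 | 25.3% | 28.5% |

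**4. Which sets this applies to.**
- *PP:* directly. Section 8.4.1 requires all criteria to be met, no section dates that judgement, and the data review meeting is not described as unaware of outcomes.
- *ITT:* not on its plain wording. The eligibility filter stands in the PP sentence and is absent from the ITT sentence, and section 5.4 points the same way. A route exists only by interpretation: ITT is limited to enrolled patients, section 4.4 enrols only those with no exclusion criterion, and section 8.2 speaks of discarded cases without defining them. Section 5.4 does not fully close this, because it concerns discontinuing the intervention while section 4.5 concerns discontinuing the patient from the study.

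**The case against.** The strongest reply is that the primary analysis is protected. The contrast between the two definitions in section 8.4.1 suggests that a treated but ineligible patient stays in ITT. Discontinuation under section 4.5 is not removal from a dataset. The discarded cases in section 8.2 are a sample-size allowance, not an analysis rule. Section 4.4 requires a chronological enrolment log and patient numbers that are not re-used, and section 4.5 requires the reason for discontinuation to be recorded, so a removed case leaves a trace. Removing eligibility violators is also the ordinary purpose of a PP set. All of this stands. A reader might infer that the plan drops failed Endorail cases from its primary result; the documents do not support that.

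A reader might also infer that these conditions can only be seen beyond the point reached at 10 minutes. That is not supported either. The documents do not say where the scope is at that time, and some conditions may be known from history or lie in segments already passed. The point is firmest for segment-level preparation and for lesions or curves proximal to the tip.

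Finally, the removal shares are assumed, and so is removal of failures only. A completed case, in which the whole colon is seen, could also be found ineligible, and removal unrelated to outcome would not inflate the error in this way.

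What the reply does not answer is the missing cut-off, the use of PP as confirmation when it can be shaped by known outcomes, and the circular meaning of *enrolled*.

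**Conclusion.** The concern holds for the PP set and, as an ambiguity only, for ITT. Because exclusions that can cause the endpoint failure may be judged after an open-label outcome, PP is open to bias in favour of the device and cannot confirm the ITT result. ITT is sound if read plainly, but the wording should not leave room for un-enrolling a treated case.

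In any set that loses failures, false success rises from 3.3% to about 7.8%, 14.6% or 25.3% with 85 treated, and from 4.2% to 7.9%, 15.4% or 28.5% with 95 treated, for assumed shares of 10%, 20% or 30%. The documents give no figure for the share. These are single-look values; the two planned interim tests are not included. The result does not need a large share: one reclassified patient can reverse a result near the boundary. This should be fixed before outcomes accrue, since a rule written afterwards would not be credible.

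**What to change.** - **Sections 4.4 and 6.2.1:** have the site confirm eligibility and enrolment in a time-stamped eCRF field before the balloon guide is inserted.
- **Section 8.4.1, ITT:** define it as every patient in whom Endorail was started, whatever is found later. Non-intubation counts as an event, and no such case is discarded.
- **Section 8.4.1, PP:** record an excluding condition first found after insertion as the reason for incompletion, not as grounds for removal. At the least, decide deviations under pre-specified rules without knowledge of the outcome, and list every removed case with its result.
- **Section 8.2:** say which cases may be discarded.
- **Reconcile** sections 4.4, 4.5, 5.4, 6.2.1, 8.2 and 8.4.1.

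These changes concern recording and analysis only, not the clinical decision to stop a procedure. The cost is protocol wording and one eCRF field. The observed incompletion rate may be slightly less favourable.

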#### **4.6 Premature Stopping of the Trial**

Both the Sponsor and the Principal Investigator reserve this right to terminate the investigation at any time. The Sponsor has the right to terminate the participation of the participant site at any time, for any reason, including but not limited to the following:

- The information on the investigational products leads to doubt as to the benefit/risk ratio;
- Patient enrolment is unsatisfactory and the patient recruitment lags behind the prospected timetable by more than 50%;
- The Principal Investigator has received from the Sponsor all investigational medical products, means and information necessary to perform the clinical study and has not included any patient after a reasonable period of time mutually agreed upon;
- Non-compliance of the Principal Investigator or Sub-investigators, delegated staff with any provision of the clinical study protocol, and breach of the applicable good clinical practice (GCP) requirements. In any case the Sponsor will notify the Principal Investigator of its decision by written notice.
- In particular, when 38 patients (40% of the sample size) and 57 patients (60% of the sample size) are reached, the significance will be tested. If significance is found, the trial can be terminated with the patients already collected.

#### **4.7 Replacements**

Patients who withdraw the informed consent before the completion of the procedure can be replaced by newly recruited patients. Similarly, for patients who are found to be lost to follow-up following the procedure completion and therefore cannot be reached by phone for the scheduled follow-up visit (Visit 2) a second and third attempt should be made after the second and third week; if the patient is still untraceable it can also be replaced by newly recruited patients (See section 5.5).

## 5. STUDY INTERVENTION

### 5.1 Identity of Investigational Products (medical device)

Endorail (Endostart s.r.l., Certaldo, Firenze, Italy) is the investigational medical device used in this study. For an extensive description of the device, please see the instruction for use.

The Endorail is composed by the following two CE marked medical devices:

- The reusable Endorail System, which consists of:
  - o The Endorail Handpiece (EH)
  - o The Endorail Cart (EC)
- The single-use Endorail Set, which consists of:
  - o The Endorail Balloon Guide (EBG)
  - o The Endorail Solution Syringe (ESS)
  - o The Endorail Powder (EP)
  - o Spike

#### Endorail Balloon Guide (EBG)

EBG is an on-demand disposable balloon catheter that can be inserted through the instrument channel of the colonoscope. EBG includes the balloon and the inflation tube. The balloon is elastic and is placed at the distal end of the catheter and its maximal capacity is 25 mL. The user may operate and control the inflation and deflation of the balloon through the syringe containing Endorail Ferromagnetic fluid connected at the proximal end of the catheter.

The balloon can be advanced ahead of the endoscope tip or pulled back through pushing/pulling action on the inflation tube at its proximal side, outside the patient's body. The EBG can be pulled back at any time during the procedure in order to allow the use of other endoscopic accessories.

